## **6.2.2      Serious Adverse Events**

An SAE must be recorded on the SAE Form. An SAE requires expeditious handling to comply with regulatory requirements. Any SAEs occurring from the signing of the ICF through 30 days after the last dose of study drug will be captured and must be reported within 24 hours after the investigator is made aware of the event.

### **6.2.2.1    Serious Adverse Event Definition**

An SAE is defined as an AE that results in any of the following outcomes:

- Death
- Is life-threatening. A life-threatening AE is any AE that places the subject – in the investigator's opinion – at immediate risk of death from the reaction as it occurred. It does not include a reaction that, had it occurred in a more serious form, might have caused death.
- Persistent or significant incapacity or substantial disruption of ability to conduct normal life functions
- Hospitalization or prolongation of existing hospitalization
- Congenital anomaly/birth defect
- Important medical events that may not result in death, be life-threatening, or require hospitalization may be considered an SAE when, based upon appropriate medical judgment, they may jeopardize the subject or may require medical or surgical intervention to prevent one of the other outcomes listed in this definition. Examples of such medical events include allergic bronchospasm requiring intensive treatment in an emergency room or at home, blood dyscrasias or convulsions that do not result in hospitalization, or the development of drug dependency or drug abuse.

Scheduled and/or elective hospitalizations occurring under the following circumstances will not be defined as SAEs for this clinical study:

- Planned before entry into the clinical study
- Elective treatment of a condition unrelated to the studied indication or its treatment
- Occur on an emergency, outpatient basis and do not result in admission (unless fulfilling the previous criteria)
- Part of the normal treatment or monitoring of the studied indication and not associated with any deterioration in condition

#### **6.2.2.2 Procedures for Reporting Serious Adverse Events**

Within 24 hours of becoming aware of ANY SAE (regardless of its relationship to investigational product) that occurs during the course of the clinical study from the time the subject signs the ICF through 30 days after the study drug is completed, the investigator must enter the SAE information into the SAE reporting system and fax supplemental data (eg, medical records or laboratory values, if applicable) to the sponsor. This ensures timely reporting of applicable reports to Health Authorities.

Note: Minimum criteria for reporting an SAE are the SAE term, an identifiable subject, a suspect investigational medical product (study drug), and a reporter. Hospitalization is not an AE, but an SAE criterion. The SAE term is the medical event that led to the hospitalization. Surgery is not an AE, but the event that required the subject to have surgery is the SAE term. Death is not an SAE, but an outcome.

The sponsor or designee will provide a FAX cover sheet for the investigators in the study reference manual.

Autopsy reports, if applicable, will be forwarded as they become available. All pertinent laboratory results should be entered on the SAE form.

All SAEs must be reported, whether or not they are considered causally related to the study drug. Appropriate clinical, diagnostic, and laboratory measures should be performed to delineate the cause of the SAE in question and the results reported. Follow-up for the SAE should occur at appropriate intervals until the event/laboratory abnormality:

- Returns to baseline or
- Becomes stable to a clinically acceptable level that is safe for the subject.

The investigator is required to assess the causal relationship of each reported SAE, to the study drug (see below). A causality assessment should always be included on the SAE form. The

investigator should make the causality assessment based on the information available at the time of the event. The causality can be updated at a future date if additional information is received.

The causality categories are:

Not related

- May or may not follow a reasonable temporal sequence from administration of the study product
- Is biologically implausible and does not follow a known response pattern to the suspect study product (if response pattern is previously known)
- Can be explained by the known characteristics of the subject's clinical state or other modes of therapy administered to the subject

Related (Possibly Related/Probably Related/Related)

- A single occurrence of an event that is uncommon and known to be strongly associated with drug exposure (eg, angioedema, hepatic injury, Stevens-Johnson Syndrome)
- Follows a reasonable temporal sequence from administration of the study product
- May follow a known response pattern to the study product (if response pattern is previously known)
- Could not be reasonably explained by the known characteristics of the subject's clinical state or other modes of therapy administered to the subject, if applicable
- Recurs upon rechallenge after withholding and then reintroducing study product

Contact information for SAE reporting and emergency contact details can be found at the beginning of the protocol and in the study reference manual.

As required by ICH guidelines and global health authorities, the sponsor or designee will notify investigators of all adverse drug reactions that are serious, unexpected, and deemed by the reporting investigator or sponsor to be related to study drug (suspected, unexpected, serious, adverse reaction [SUSAR]). Causality, while assessed, does not negate reporting requirements to the sponsor. An AE, whether serious or not serious, is designated unexpected (unlabeled) if it is not reported in the clinical safety section of the Investigator Brochure (IB) or if the event is of greater frequency, specificity, or severity than is mentioned in the IB. The investigator will receive a copy of the current valid version of the IB prior to the start of the study; however, the investigator will not be required to assess expectedness, nor should expectedness impact the investigator reporting SAEs within the timeframe herein defined.

Upon receiving such notices, the investigator must review and retain the notice. If it is determined that there is an unanticipated signal, the NPS SMT will analyze the data and prepare a summary supporting the determination and interpretation of the findings. The sponsor or designee will send this summary to the investigators with instructions to provide it to their Institutional Review Board (IRB).

The investigator should also comply with the IRB procedures for reporting any other safety information (ie, autopsy reports).

NPS Pharmaceuticals, Inc. or its designee will be responsible for submitting SUSAR reports to the appropriate health authorities. These reports will be submitted within the expedited timeframe.

### **6.2.3      Pregnancy Reporting**

In the event a subject becomes pregnant during the study, study drug will be discontinued and an SAE form will be completed to capture potential drug exposure during pregnancy. This will be reported within 24 hours of becoming aware of the pregnancy. The subject will be followed up until an outcome is known (ie, normal delivery, abnormal delivery, spontaneous abortion [miscarriage], voluntary abortion, or therapeutic abortion). If a pregnant subject also experiences an SAE, an additional SAE form will be completed and submitted within 24 hours as discussed above.

In the event a female partner of a male subject becomes pregnant within 30 days after the subject completes the trial and she or the fetus experiences an SAE, the SAE is deemed “suspected” to study drug by the principal investigator (PI) and a supplemental SAE form will be completed to capture the event.

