#### **6.2.6 Women of Child Bearing Potential**

Women of childbearing potential who are younger than 55 years or are not surgically sterile must have a negative urine pregnancy test result at screening and baseline to be enrolled. Pregnancy tests will also be performed at each on-treatment study visit. Sexually active WOCBP and partners of male subjects must use highly effective and medically acceptable methods of birth control during and for 30 days after the treatment period (ie, abstinence, oral contraceptive pills with barrier methods and spermicide, transdermal or injectable contraceptives, intrauterine device, surgical sterilization of partner), in a manner such that the risk of failure is minimized. The investigator will discuss which methods the subject will prefer to use. For a woman to be considered postmenopausal, at least 2 years must have elapsed since her last menses.

At the time of signing the ICF, WOCBP must be advised of the importance of avoiding pregnancy during trial participation, and the potential risk factors for pregnancy. Male subjects must be advised that their partners must use medically acceptable methods of birth control during and for 30 days after the treatment.

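### Protocol 6.2.3 covers partner pregnancies only if they begin in the 30 days after a male subject completes the trial, while 6.2.6 requires partner contraception throughout dosing and for 30 days after it

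*Protocol*

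**What the plan says.** Section 6.2.3 (Pregnancy Reporting) has two rules.

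- **Female subjects.** "In the event a subject becomes pregnant during the study, study drug will be discontinued and an SAE form will be completed". The report is due within 24 hours of awareness, and "The subject will be followed up until an outcome is known".
- **Partners of male subjects.** The rule applies when a partner "becomes pregnant within 30 days after the subject completes the trial and she or the fetus experiences an SAE". The SAE is then treated as suspected to be due to study drug, and "a supplemental SAE form will be completed to capture the event".

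Section 6.2.6 (Women of Child Bearing Potential) sets the contraception period for both groups, with the 30 days counted from the end of treatment: "Sexually active WOCBP and partners of male subjects must use highly effective and medically acceptable methods of birth control during and for 30 days after". It repeats the point for men: "Male subjects must be advised that their partners must use medically acceptable methods of birth control during and for 30 days after the treatment".

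The general SAE rule in 6.2.2 runs "from the signing of the ICF through 30 days after the last dose of study drug".

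The protocol file holds several successive versions. Sections 6.2.3 and 6.2.6 are worded the same on these points in the three versions that show them. The newest version breaks off in its summary.

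**The concern.** The contraception requirement in 6.2.6 shows when the protocol regards a partner's conception as a possible exposure: while the man is being dosed and for 30 days afterwards. The reporting rule in 6.2.3 should cover the same span. As written, it opens only when dosing is over.

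The causality provision makes this odd. An SAE after a conception that began once the trial was complete is presumed suspected to be due to the drug. The same SAE after a conception during daily dosing has no pregnancy-reporting rule at all.

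A site that follows the text would have no instruction to report an on-treatment partner pregnancy, even one with a serious outcome. A study report with no partner events from the dosing period could then reflect the window rather than what happened.

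**Working it through.** The plan states no figure for this point. The check compares the two windows and then sizes the gap.

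**Windows side by side (partners of male subjects)**

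| Period | Contraception required (6.2.6) | Partner event reportable (6.2.3) |
|---|---|---|
| Stage 2 dosing | yes | no |
| Stage 3 dosing | yes | no |
| 30 days after dosing ends | yes | yes, if the subject completed the trial and an SAE follows |

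**Length of the uncovered period**

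Inputs: Stage 2 is 24 weeks (3.1); Stage 3 is at most a further 24 months (3.2); the tail is 30 days (6.2.6). A month is taken as 30.4375 days, and completion of the trial is taken to coincide with the end of dosing.

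- Stage 2: 24 × 7 = 168 days.
- Stage 3, maximum: 24 × 30.4375 = 730.5 days.
- Maximum dosing: 168 + 730.5 = 898.5 days, and 898.5 / 365.25 = 2.46 years.
- Contraception period: 898.5 + 30 = 928.5 days.
- Share inside the partner rule: 30 / 928.5 = 3.2%.

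Stage 3 can end sooner if the product becomes commercially available. In the extreme case where it adds nothing, the contraception period is 168 + 30 = 198 days and the share is 30 / 198 = 15.2%. The share therefore lies between 3.2% and 15.2%, and the on-treatment part covered is zero throughout.

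**Does another rule fill the gap?**

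- The SAE window in 6.2.2 does include the dosing period. However, 6.2.1.1 defines an adverse event in a subject given the product, and the minimum criteria in 6.2.2.2 call for an identifiable subject. A partner is neither enrolled nor dosed.
- Congenital anomaly is among the SAE criteria in 6.2.2.1, but it qualifies an adverse event as so defined. It does not extend the definition to partners.
- The pregnancy tests in Tables 6-1 to 6-3 are for women enrolled in the study.

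No section shown clearly provides for a partner conception during dosing.

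**Where exposure lies**

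Section 1.1 gives an elimination half-life of about 2 hours. The period that 6.2.3 covers is therefore one in which the man is no longer exposed, and the period it leaves out is the one with daily dosing.

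**The case against.** Several points on the other side have weight.

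- **Drafting slip.** The authors may have meant the 30 days as an outer limit, covering everything up to that point. That is plausible, but the text does not say so, and sites follow the text.
- **Little is at stake.** Section 1.1 reports no effect on sperm parameters, reproductive performance or early embryonic development in rats, no increase in malformations in rats and rabbits, and negative genotoxicity studies. The trial plans at least 5 subjects of both sexes. This keeps the point modest, but it does not reconcile the two sections.
- **The current text is not visible.** Other sections did change between versions, so this one may have changed too. That stands as a limit on confidence.

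A reader might infer more than the documents support:

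- **That the female rule leaves out the 30 days after treatment.** It does not do so expressly. The study is not bounded for each subject: 6.2.2.2 describes SAEs in the course of the study as running to 30 days after study drug, and section D (Duration of the Study) puts study end at database lock. The window is unstated rather than too short.
- **That exposure in female subjects is not followed during dosing.** It is. Sections 6.2.6 and 6.2.3 provide on-treatment pregnancy tests, prompt reporting and follow-up to outcome.
- **That a conception too recent for the final urine test escapes the rule.** It began during the study and is reportable whenever the site learns of it.
- **That men who withdraw early are excluded.** This follows only from a literal reading of completion.

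**Conclusion.** The partner window in 6.2.3 does not match the contraception period in 6.2.6 and should be corrected. On the literal text, all partner conceptions during dosing, up to about 898 days, fall outside the reporting rule, and only the 30 days after completion fall inside it. The 898 days is a maximum. The 3.2% is a share of calendar time and says nothing about how often a pregnancy would occur.

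For female subjects the matter is one of clarity: the 30-day tail should be stated, but the documents do not exclude it.

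Nothing in the protocol promises that partner pregnancies without an SAE will be recorded and followed to outcome, so their absence contradicts nothing. Collecting them would be a choice, not a correction.

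The conclusion assumes that the section stands unchanged in the newest version, which is cut off before it. Confidence is therefore moderate.

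**What to change.** Reconcile 6.2.3 with 6.2.6:

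- Let the partner rule apply to any conception from the male subject's first dose through 30 days after his last dose, whether or not he completed the trial.
- State for female subjects that the reporting period includes the 30 days after the last dose, as a clarification of the present wording.
- As an option, record partner pregnancies without an SAE and follow them to outcome, with the partner's consent.

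The first two items cost about two sentences in an amendment. The third would add a partner consent form. First check whether the newest protocol version already contains the change. No dose, visit or treatment rule is affected.

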### **6.2.4      Laboratory Evaluations**

Laboratory results can vary depending on whether samples are drawn on an on- or off-PN/I.V. day, so it is important that every effort be made to draw laboratory samples on the same type of infusion day (ie, on- or off-PN/I.V.) throughout the study. Although subjects do not need to be in a fasted state at the time of their clinic visit, they should avoid large meals or large volumes of fluid, including PN/I.V. with lipids, within 3 hours of the clinic visit to permit consistent assessment. If peripheral venous access is not possible, the sample may be drawn from the central line. A home nursing visit may be appropriate to collect samples in some circumstances. The site’s clinical laboratory will centrifuge and send the samples to the central lab, SRL Medisearch Inc. SRL Medisearch will analyze those specimens while sending the citrulline, antibody, and PK samples to NPS headquarters in the U.S.

Clinically significant (as determined by the investigator) abnormal laboratory test results will be considered AEs, if they are not related to the subject’s underlying condition or their previous comorbid medical history (unless they are a worsening of the condition). A result outside of the

normal range may be repeated for confirmation. Any laboratory test result that meets the criteria for an SAE (Section 6.2.2) must also be recorded in an SAE Form so that the sponsor or designee can collect additional information about that abnormality, including information regarding relationship to investigational product or other causes, any action taken, and outcome.

The following laboratory parameters will be collected according to the Schedule of Evaluations and Procedures outlined in [Table 6-1](#), [Table 6-2](#) and [Table 6-3](#).

### **Hematology**

Hemoglobin, hematocrit, erythrocyte count, platelet count, and leukocyte count with differential

### **Serum chemistry**

Albumin; alkaline phosphatase; ALT; amylase; AST; total, direct, and indirect bilirubin; blood urea nitrogen; calcium; chloride; total-cholesterol; C-reactive protein; creatinine; creatinine clearance; gamma glutamyl transferase; glucose; lipase; magnesium; phosphate; potassium; sodium; triglycerides; and uric acid

### **Urinalysis**

Blood, glucose, leucocytes, microscopic, pH and osmolality, protein, and sodium

### **Pregnancy test**

Urine pregnancy test (women of childbearing potential [WOCBP] only)

### **Antibodies to teduglutide and ECP**

Blood samples for analyses of antibodies to teduglutide and to ECP will be collected at baseline and at Weeks 12 and 24 or early termination during Stage 2 of the study, and at Months 6 and 12, and at the final visit or early termination in Stage 3.

If teduglutide-specific antibodies are detected, subjects may remain in study and will continue to be tested at each visit, as long as there are no concurrent AEs associated with immunogenicity.

Subjects who test positive for teduglutide-specific antibodies at the end of Stage 2 will be allowed to enter Stage 3, as long as there are no concurrent AEs associated with immunogenicity. The presence of teduglutide-specific antibodies will continue to be monitored at every visit until the end of this study. If, at the final visit, the subject is still positive for teduglutide-specific antibodies, the subject will require follow-up blood draws as specified above. If any subject (previously negative for teduglutide antibodies) has specific anti-teduglutide antibodies at the final visit of this study, they will have follow-up blood draws for antibodies at Months 2, 3 and 6 post-study. These may be done at a local laboratory convenient to the subject, however all blood samples will be mailed to the central laboratory for analysis. If a subject's results are negative at 2 successive visits within this time, follow-up may be terminated. If at the end of 6 months the subject is still determined to have

teduglutide-specific antibodies, the PI and the sponsor will determine if additional follow-up may be required. During this follow-up, subjects will be evaluated for AEs or SAEs related to immunogenicity, which will be collected in the Pharmacovigilance database. Collection of AE and/or SAE information may be done via telephone contact.

### **Teduglutide Concentrations**

Teduglutide concentrations will be determined in the blood samples collected for antibody testing, ie, at baseline and at Weeks 12, 24 or early termination during Stage 2 of the study, and at Months 6, 12, and at the final visit or early termination in Stage 3.

#### **6.2.5 Plasma Citrulline**

Plasma citrulline will be measured as an assessment of enterocyte mass, according to the Schedule of Evaluations and Procedures ([Table 6-2](#) and [Table 6-3](#)). If peripheral venous access is not possible, blood samples for citrulline may be drawn from a central line. The samples will be processed according to instructions in the laboratory manual.

#### **6.2.6 Women of Child Bearing Potential**

Women of childbearing potential who are younger than 55 years or are not surgically sterile must have a negative urine pregnancy test result at screening and baseline to be enrolled. Pregnancy tests will also be performed at each on-treatment study visit. Sexually active WOCBP and partners of male subjects must use highly effective and medically acceptable methods of birth control during and for 30 days after the treatment period (ie, abstinence, oral contraceptive pills with barrier methods and spermicide, transdermal or injectable contraceptives, intrauterine device, surgical sterilization of partner), in a manner such that the risk of failure is minimized. The investigator will discuss which methods the subject will prefer to use. For a woman to be considered postmenopausal, at least 2 years must have elapsed since her last menses.

At the time of signing the ICF, WOCBP must be advised of the importance of avoiding pregnancy during trial participation, and the potential risk factors for pregnancy. Male subjects must be advised that their partners must use medically acceptable methods of birth control during and for 30 days after the treatment.

#### **6.2.7 48-Hour Oral Fluid Intake and Urine Output**

Subjects will be provided with urine collection containers (as needed) in order to collect 48-hour urine during the 2 days prior to each study visit at which this is required (all visits during Stages 1 and 2 and at the visits specified in [Table 6-3](#) during Stage 3). The center staff will contact the subject at least 48 hours before the scheduled visits to remind the subject to start measuring complete I/O, and to record these measurements into the diary. At these times of

48-hour measurements, oral fluid intake must remain as stable as possible compared with baseline. These measurements will also be collected at any required interim safety visit.

### **6.2.8 Clinical Assessment of Crohn's Disease Activity**

Any subject enrolled in the study with a history of Crohn's disease will have clinical status assessed at screening and again at the baseline visit in Stage 2 to determine whether the subject has active or quiescent disease. Subjects with active Crohn's disease are excluded from study participation; therefore, endoscopy/colonoscopy prior to study treatment may be required in subjects with clinical suspicion of active disease. In addition, upper GI contrast series with small bowel follow-through is required in subjects with a history of Crohn's disease to detect any clinically significant active stenosis and/or active stricturing that may need to be addressed.

